We will systematically approach the challenge associated with the quantitative neurobiological study of co-addiction. We thoroughly characterize four subject groups demographically, clinically, cognitively and neurally. In order to construct the model, we will integrate several readily quantifiable aspects of brain function in individuals addicted to either alcohol, nicotine, both or neither. **SA1** uses the capabilities of the Advanced Imaging Research Center (AIRC) at Oregon Health & Science University (OHSU, VAPORHCS affiliated university) to obtain measures of task based neural activation, functional and anatomical connectivity and cortical density. Our preliminary data demonstrate that we can use functional and anatomical neuroimaging to differentiate groups who primarily use either nicotine or alcohol from both each other and from non-addicted control subjects (CS). Importantly, **Preliminary Study 1** demonstrates that neural response on a Probability/Delay Discounting task (PDD) differentiates individuals who remain abstinent after initial sobriety from alcohol and those who do not. **SA2** will use the data generated by **SA1** to develop the predictive multidimensional neural model and leverage our understanding of the cerebral basis of AUD and NUD to differentiate co-addicted vs. singly addicted individuals and to use neurobiological markers to predict success during early recovery.

SA 1: Test a dual network model of alcohol and nicotine co-addiction via contrast of multiple neural aspects of AUD, NUD, NAUD and CS: a) task based (PDD) and stress modulated cue induced craving, b) volumetric estimates of cortical density (voxel-based morphometry [VBM]), c) anatomical (diffusion tensor imaging [DTI]) and d) resting state functional connectivity.

Hypothesis 1a.1: **We hypothesize** that individuals co-addicted to alcohol and nicotine will exhibit a pattern of cortical activation to delay, magnitude and probability characterized by both increased sensitivity to reward in striatum and aversion to risk and delay in dorsal cognitive control regions. **(1a.2) Furthermore**, differences in neural activity between stressed and unstressed drug associated stimuli (DAS) will identify regions associated with cognitive control of DAS. We predict that parametric variation in cortical structures hypothesized to control response to DAS, will show greater stress-induced variation when the DAS represent the preferred substance.

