Hypothesis 1b: **We hypothesize** that connections within the decision making network will exhibit both anatomical (measured by DTI and VBM) and functional disruption in NAUD, AUD and NUD groups relative to CS. We predict that alcohol and nicotine use are associated with greater cortical (cingulate and prefrontal cortex) thinning and decreased white matter integrity in superior and inferior longitudinal fasciculi and rostral trans-callosal fibers.

SA 2: Develop a machine learning model that integrates behavioral, task and resting state functional activation, volumetric data and structural connectivity that a) differentiates the four groups and b) predicts treatment outcome at 3 months.

Hypothesis 2a: **We hypothesize** that a support vector machine (SVM) learning paradigm can exploit the substantial differences in quantitative neuroimaging measures among NAUD, AUD, NUD and CS groups (obtained in **SA1**) to construct and validate a quantitative classifier that predicts group membership. The classifier will produce a neural model that offers insight into the specific neuroadaptations that occur in co-addiction.

Hypothesis 2b: **We hypothesize** that an SVM classifier can be used to predict treatment outcomes and provide intermediate phenotypes that can be used in future treatment studies. We predict that co-addiction to nicotine is an additional risk for alcohol relapse and make a primary prediction that subjects in the NAUD group will be more likely to relapse than AUD only. Secondarily, we expect that subjects who maintain sobriety will show decreases in responsivity to reward characteristics and show recovery from decreased cortical density and fractional anisotropy. We further hypothesize that comparison of imaging measures at baseline and three months will find recovery associated with improved pre-frontal cortical structural and functional integrity.

[name]

Version date: 2-1-2021

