linear kernel) and requires selection of parameters characteristic of each kernel and a constant, C, that characterizes the error penalty. Our approach (schematic in **Figure 3**) to a machine learning model (Schoelkopf and Smola, 2001) closely follows the method of Ding et al. (2015). **Feature extraction:** The first step in this analysis is extraction of features from the functional, resting state, volumetric and white matter connectivity datasets that will be used in the Support Vector Machine. We plan an ROI based analysis (e.g., see **Table 3**). This set of regions will be adjusted and expanded after preliminary analysis of functional and anatomical measures that statistically separate the four groups. Specifically, we use the following suitably scaled features: 1) average cortical density in the ROIs extracted from VBM; 2), average FA in white matter tracts connecting the ROIs (from atlas tract-based spatial statistics (TBSS)), 3) rsMRI connectivity correlation matrices between ROIs, 4) regional parametric regressor means and 5) clinical and demographic variables.

C6a. Classification of AUD, NUD, NAUD and CS (SA2a): The method can be extended to multigroup classification [see, e.g., (Hsu and Lin, 2002; Forkert et al., 2015); (Lajnef et al., 2015), albeit with somewhat greater complexity. LIBSVM uses the “one-against-one” method, which essentially approaches the problem as multiple binary classification problems (there are 6 binary classifiers for 4 groups). We will use the same set of features as above, but the rank order of features may differ.

C6b. Three-month outcome (SA2b): For the outcome predictor, cigarettes per day and pack-years will be added as a feature. We cross-validate the model using a bootstrapping procedure (**Figure 3**). We plan on testing a range of kernels such as the linear, polynomial, radial, and sigmoid kernels. The data will be divided into a training set and a test set (70%/30% split, stratified by relapse status). For each kernel type, we will use 10-fold cross-validation within the training set to determine optimal parameters amongst a wide range of

values. The SVM’s with the optimal parameters will then be applied to the test set. This procedure will be simulated 10,000 times, from which an optimal kernel and corresponding parameters will be selected.

C6c. Expected Outcomes and Alternatives:

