We will examine the performance of the SVM classifier by calculating sensitivity, specificity and balanced accuracy. Sensitivity = $TP/(TP + FN)$, Specificity = $(TN/(TN+FP))$ and Balanced Accuracy = $(1/2)(TP/(TP+FN) + TN/(TN+FP))$, where TP is true positive, FP is false positive, FN is false negative, and TN is true negative. The model will be especially useful if balanced accuracy reaches ~70%. If accuracy is below this number, we will investigate refinements or alternatives to our model building techniques. If SVM methods still prove intractable, we are currently developing alternative methods including a random forest approach and multivariate distance matrix regression [MDMR (Zapala and Schork, 2012)]. These methods have

$$\begin{aligned}
 1.1 \quad V_p &= \frac{M}{(1+kt)} \quad V_p = \frac{M}{(1+h\theta)} \\
 1.2 \quad V_p &= \frac{M}{(1+kt)(1+h\theta)} \Rightarrow \frac{20}{M} = \frac{1}{(1+kt)(1+h\theta)} \\
 1.3 \quad V'_{uc} &= \frac{V_{uc}}{V_{tot}} = \frac{1}{1 \cdot 12 \cdot 3} \int_0^{12} \int_0^3 \frac{dt d\theta}{(1+kt)(1+h\theta)} = \\
 &= \int_0^{12} \frac{dt}{12(1+kt)} \int_0^3 \frac{d\theta}{3(1+h\theta)} = \frac{A_k}{12} \frac{A_h}{3} = A'_k A'_h
 \end{aligned}$$

Figure 2: Analysis of discounting tasks. V_p is the immediate value of the amount M , available after delay, t or odds against, θ = $(1-p)/p$, where p is the probability of receiving the reward.

V'_{uc} is the fractional volume under the discounting surface.

been used to classify individuals with addiction [(Squeglia et al., 2016), random forest] and ADHD [(Yang et al., 2016), MDMR].

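### The outcome SVM is judged only as a combined model, with no non-imaging comparator to show what imaging adds beyond clinical, demographic and smoking features

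*Combined protocol and SAP*

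**What the plan says.** All references are to the combined protocol and SAP.

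- **Aim.** Section 2 (Specific Aims) says the study will "use neurobiological markers to predict success during early recovery". Hypothesis 2b adds that "an SVM classifier can be used to predict treatment outcomes and provide intermediate phenotypes that can be used in future treatment studies".
- **Features.** C6 lists cortical density, FA in connecting tracts, resting-state connectivity, and then "4) regional parametric regressor means and 5) clinical and demographic variables". All of these enter one vector. For the three-month outcome model, C6b states that "cigarettes per day and pack-years will be added as a feature".
- **Performance mark.** C6c reports sensitivity, specificity and balanced accuracy, and says "The model will be especially useful if balanced accuracy reaches ~70" per cent. If the model falls short, the plan is to refine it or to try random forest or MDMR. Those steps change the algorithm. They do not separate the contributions of the feature types.
- **Smoking as a risk factor.** Under Hypothesis 2b the investigators "make a primary prediction that subjects in the NAUD group will be more likely to relapse than AUD only". C6d lists smoking co-addiction beside the neural measures as an expected predictor of poor outcome.
- **Who is followed.** C1 limits follow-up to AUD and NAUD. Table 1 requires fewer than 20 lifetime cigarettes in AUD (C2 allows a change to 100 if recruitment is difficult) and current smoking in NAUD.

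The visible text specifies no clinical-only, smoking-only or imaging-only model, no ablation, and no comparison of accuracy with and without imaging.

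**The concern.** The study wants to say something about neural markers of relapse, but the only performance figure it plans for the outcome classifier belongs to a model that also holds clinical, demographic and smoking data. AUD subjects have effectively no smoking exposure and NAUD subjects all smoke, so cigarettes per day and pack-years come close to a group label. If the plan's own prediction about group and relapse is right, that label carries predictive signal before any scan is used.

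The imaging features are also expected to differ between the groups (C6d), so they may partly stand in for smoking status. A good combined accuracy would then be compatible with a large, small or absent contribution from imaging, and the planned output would not tell a reader which.

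**Working it through.** **The plan's own figure.** The 70% is a chosen target with no derivation, so there is nothing to reproduce. The power figures in C8 concern an AUD-versus-CS fMRI contrast and do not bear on the classifier.

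**Inputs from the documents.** 50 subjects per group (C8); follow-up in AUD and NAUD only (C1), hence at most 50 + 50 = 100 subjects; a 70%/30% split (C6b), hence about 70 training and 30 test subjects before dropout.

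**Assumed input.** Relapse proportions pA (AUD) and pN (NAUD). The documents give none, so a range is used.

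**Step 1: smoking status alone.** Predict relapse for every NAUD subject and abstinence for every AUD subject. With equal groups:

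- sensitivity = pN / (pN + pA)
- specificity = (1 − pA) / [(1 − pN) + (1 − pA)]
- balanced accuracy = half their sum

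| pA / pN (assumed) | Sensitivity | Specificity | Balanced accuracy |
|---|---|---|---|
| 40% / 60% | 0.60/1.00 = 0.60 | 0.60/1.00 = 0.60 | 0.60 |
| 35% / 65% | 0.65/1.00 = 0.65 | 0.65/1.00 = 0.65 | 0.65 |
| 30% / 70% | 0.70/1.00 = 0.70 | 0.70/1.00 = 0.70 | 0.70 |
| 30% / 50% | 0.50/0.80 = 0.625 | 0.70/1.20 = 0.583 | 0.60 |
| 30% / 60% | 0.60/0.90 = 0.667 | 0.70/1.10 = 0.636 | 0.65 |

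Chance is 0.50, so the distance to the mark is 0.20. Smoking status covers 0.10/0.20 = half of it at 40%/60%, 0.15/0.20 = three quarters at 35%/65%, and all of it at 30%/70%.

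**Step 2: smoking status plus one clinical score, no imaging.** A simulation combined group with one normal score separating relapsers from abstainers by d standard deviations, using the ideal rule. With d = 0.8 to 0.9, balanced accuracy is 0.70 to 0.71 at 30%/60%, and 0.67 to 0.69 at 40%/60%. These are ideal values; a rule fitted to about 70 subjects would usually do somewhat worse.

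**Step 3: how precisely the increment could be estimated.**

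- The 95% half-width around 0.70 is 1.96 × 0.5 × √(0.21/n₁ + 0.21/n₀), where n₁ and n₀ are the relapsers and abstainers in the test set. With 15 and 15 it is 0.164; with 9 and 21 it is 0.179.
- For the paired difference a McNemar-type normal approximation was used, treating balanced accuracy as accuracy and assuming that 15% to 30% of subjects are classified differently by the two models.

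| Full vs non-imaging | Power, 30 test subjects | Power, all 100 subjects |
|---|---|---|
| 0.70 vs 0.60 | 0.16–0.29 | 0.45–0.74 |
| 0.70 vs 0.65 | 0.07–0.10 | 0.15–0.25 |

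**The case against.** **Integration is the purpose.** SA2 sets out to combine behavioral, imaging and connectivity data, and nowhere does the plan claim superiority over clinical data. This stands: including smoking and clinical features is not an error.

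**The 70% is only a mark of usefulness.** C6c does not call it a test of neural prediction. This also stands. The gap is between that mark and the aim in section 2, for which no other measure of classifier performance is given.

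**Other analyses may speak to imaging.** C6a mentions a rank order of features, Figure 3 is not shown, and the cited workflow cannot be consulted. The plan also includes a direct NAUD-versus-AUD relapse prediction, a baseline-to-three-month imaging comparison related to recovery, and exploration of how imaging depends on severity of use (C1). A reader might infer that the trial can neither support nor refute any neural claim; because of these analyses, the documents do not support that. But ranking describes weight within one model, and none of the other analyses measures accuracy gained over non-imaging data.

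**The relapse rates are assumed.** A reader might infer that smoking alone will meet the mark. Hypothesis 2b predicts a direction, not a size. Among the symmetric scenarios shown, only 30%/70% reaches 0.70, which is a 40-point difference and an odds ratio of (0.7/0.3)/(0.3/0.7) ≈ 5.4.

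**The comparison is weak.** Step 3 confirms low power. In addition, smoking may act through the brain changes being measured, so a null increment would not refute a neural marker. Both points limit how the increment may be used; neither is a reason to omit it.

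**Conclusion.** The concern holds as a missing comparator. The outcome SVM is judged by combined-model balanced accuracy alone, and the visible plan has no analysis of what imaging adds to clinical, demographic and smoking features. Under the assumed relapse rates, smoking status alone gives a balanced accuracy of about 0.60 to 0.70, so between half and all of the distance from chance to the 70% mark could be covered without imaging. The upper end needs an extreme contrast between the groups.

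The result rests on equal groups of 50, on smoking variables that nearly encode group, and on relapse rates that the documents do not give. It does not show that imaging lacks value, that combining features is wrong, or that 70% will be reached without scans. It means that combined accuracy alone should not be presented as evidence that neural markers add predictive value.

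**What to change.** 1. Prespecify a comparator SVM using only the clinical and demographic features plus cigarettes per day and pack-years. List those features by name, and state whether the behavioral measures belong to the comparator or only to the full model.
2. Run it through the same training/test splits, kernels and tuning as the full model.
3. Report the paired difference in balanced accuracy (full minus non-imaging) with an interval obtained by resampling subjects, keeping repeated copies of a subject on the same side of any split. The spread across the 10,000 splits should not serve as the interval: the splits overlap, so their spread is not sampling error.
4. Label the increment exploratory. State that combined accuracy alone will not be offered as evidence of added neural value, and that a null increment does not rule out a neural marker, because smoking may act through the measured brain changes.

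The cost is extra computing, with no new subjects, scans or visits. The drawback is an imprecise estimate with at most 100 subjects, which the interval will make visible.

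### C6b appears to choose the SVM kernel on the same test sets that would supply its accuracy; the choice should be made inside the training data (likely optimism about 1 to 2 points)

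*Combined protocol and SAP*

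**What the plan says.** Section C6b sets out the outcome classifier in five steps.

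- Several kernels compete: "We plan on testing a range of kernels such as the linear, polynomial, radial, and sigmoid kernels".
- There is one two-way division, with no third part: "The data will be divided into a training set and a test set (70%/30% split, stratified by relapse status").
- Tuning is internal to the training part and separate for each kernel: "For each kernel type, we will use 10-fold cross-validation within the training set to determine optimal parameters amongst a wide range of" candidate settings.
- Evaluation on held-out subjects comes next: the tuned classifiers "with the optimal parameters will then be applied to the test set".
- Finally: "This procedure will be simulated 10,000 times, from which an optimal kernel and corresponding parameters will be selected".

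Section C6c follows with the evaluation: "We will examine the performance of the SVM classifier by calculating sensitivity, specificity and balanced accuracy". It does not say on which data these are computed. It gives a benchmark, "The model will be especially useful if balanced accuracy reaches ~70" per cent, and a rule for falling short: "If accuracy is below this number, we will investigate refinements or alternatives to our model building techniques".

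Neither section describes an outer validation loop, a locked hold-out set or an external cohort. Figure 3, which draws the scheme, is not available in the text reviewed.

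**The concern.** Tuning parameters inside the training part is sound. The difficulty is the last step. Applying the tuned models to the test set is the final action in the repeated procedure, so choosing a kernel from the repeats most naturally means choosing it on test results. If the winner's test accuracy is then quoted as the model's accuracy, the same results have been used to select and to evaluate, and the quoted value is biased upwards.

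The wording also covers parameters. These are re-tuned in every split, so after 10,000 repeats a kernel has no single parameter set. Fixing one needs a further choice, and the plan gives no rule for it. Some possible rules carry more bias than others.

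At stake is how to read the balanced accuracy for relapse prediction. Predicting relapse or recovery is one of the two purposes in the Specific Aims, and the figure will be set beside the benchmark of about 70%. The rule in C6c for refining or replacing the model could add further optimism if it is applied on the same data. That effect was not simulated.

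**Working it through.** The documents give no expected accuracy, sample size or power for this classifier (C8 concerns fMRI group contrasts), so there is no stated figure to reproduce. The check is the size of the bias when there is nothing to find.

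**Inputs from the documents**
- 50 subjects per group (C8). Only NAUD and AUD are followed (C1, payment paragraph), so at most 2 × 50 = 100 subjects before dropout.
- Test set: 0.30 × 100 = 30 subjects.
- Four named kernels, 10-fold inner tuning, 10,000 repeats (C6b).

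**Assumed, because not given:** relapse rate 30% to 50%, 50 to 300 features, 80 to 100 subjects analysed. Table 3 lists 10 bilateral regions plus the brainstem, so 21 regions and 21 × 20 / 2 = 210 connectivity pairs. The upper part of the feature range is therefore the more realistic.

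**Precision of one test set**
- SE of accuracy at chance = √(0.25 / 30) = 0.091.
- Chance of at least 21 of 30 correct (70%) by guessing: binomial tail = 0.021.

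**Use of subjects across repeats**
- Probability that a given subject is never in a test set = 0.7^10,000, effectively 0. Every subject feeds the final selection.

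**Null simulations.** True balanced accuracy was 0.50, features were fixed pure noise, splits were stratified 70/30, and a least-squares SVM stood in for LIBSVM.
- Set A: 100 subjects, 50 features, 4 kernels × 5 penalties, 60 datasets × 60 splits at each of 50% and 30% relapse.
- Set B1: 100 subjects, 100 features, 50% relapse, 60 datasets × 60 splits.
- Set B2: 80 subjects, 300 features, 40% relapse, 40 datasets × 40 splits.
- Sets B1 and B2 used 12 kernel settings × 3 penalties = 36 combinations. A combination was eligible only if inner tuning had chosen it in at least 5% of splits (minimum 3).

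| What is reported | Set A | Set B1 | Set B2 |
|---|---|---|---|
| No selection on test results | 0.50 | 0.502 | 0.499 |
| Best of four kernels by mean test accuracy | 0.513–0.515 | 0.515 | 0.516 |
| Best kernel-and-parameter combination by mean test accuracy | 0.536–0.540 | 0.565 | 0.560 |

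The first row is full selection inside the training part for Set A, and the average over the four tuned kernels for Sets B1 and B2. The Monte Carlo SE of the best-kernel means in B1 and B2 is 0.005 and 0.007.

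Bias against 0.50:
- Best kernel: 0.513 − 0.50 = 0.013 to 0.516 − 0.50 = 0.016.
- Best combination: 0.536 − 0.50 = 0.036 to 0.565 − 0.50 = 0.065. This reached 0.60 or more in 13% (B1) and 25% (B2) of null datasets, and 0.70 in none.

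**Best single split of 10,000**
- 16 null datasets, linear kernel: averages of 0.79 to 0.81, range 0.75 to 0.87.
- 4 further null datasets, four kernels with fixed parameters: 0.70, 0.80, 0.83 and 0.83.

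**Why the best-kernel bias is small.** The kernels are scored on the same splits, so their means move together. In one of the four fixed-parameter datasets they were 0.483, 0.485, 0.486 and 0.482: the best exceeds their average of 0.484 by only 0.002. Variation between datasets is larger: the SD of the best-kernel mean was 0.035 (B1) and 0.044 (B2).

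**The case against.** The strongest reply is that the plan nowhere says test results do the selecting. Inner cross-validation scores, or how often a setting wins, would also fit the wording, and the missing figure may settle it. C6c is equally silent on the evaluation data, so reuse is inferred. This stands, and the point is therefore conditional. It does not remove the need to act: if inner scores pooled over all repeats were used, every subject would still have entered the choice, and the text would still not say where the reported accuracy comes from.

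A reader might infer that no unbiased estimate is possible because every subject is a test subject many times. The documents do not support that. For any one kernel, tuning stays in the training part, and the mean test accuracy over 10,000 splits is ordinary repeated hold-out. Recurrence across splits is not leakage. Bias enters when a winner is picked on those means and its own mean is reported.

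A reader might also infer that pure noise would pass the 70% benchmark. That requires reporting the single best split, which the plan does not state. Moreover, C6c presents about 70% as a level of particular usefulness, not as a formal success test.

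Finally, the primary prediction under Hypothesis 2b, more relapse in NAUD than in AUD, does not depend on the kernel.

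**Conclusion.** The concern holds in conditional form. On the natural reading, C6b selects the kernel on test-set performance, and C6c reserves nothing from which to report an untouched accuracy. If the winner's test accuracy is reported, it is too high by about 1 to 2 points for the best of four kernels by mean test accuracy, the best-supported reading. It is too high by about 4 to 6 points if kernel-and-parameter combinations are also chosen on test results. The worst case, 0.70 to 0.87 from noise, needs a rule that is not in the text.

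The direction of the bias is secure. Its size rests on the assumed feature counts, relapse rates and numbers analysed, on the stand-in classifier, and on limited simulation runs. The kernel-and-parameter figure is the more sensitive: the two sets of runs gave about 4 and about 6 points. This should be fixed before the outcome model is run, but it does not undermine the study design or the NAUD-versus-AUD relapse comparison.

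**What to change.** In C6b, treat kernel type as one more tuning parameter. Within each split, choose kernel and parameters together by the 10-fold cross-validation inside the 70% training set, on a named metric such as balanced accuracy. Apply only that winner to the 30% test set. In C6c, state that the reported balanced accuracy, sensitivity and specificity are the means for this whole procedure over the splits.

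A final model may then be refitted on all subjects, but its accuracy should not be taken from the selection step. If the C6c refinement rule is used, evaluate any refinement in the same nested way and report the initial result beside it. A p-value from repeating the procedure on shuffled relapse labels is optional.

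The cost is a rewritten paragraph in C6b, a sentence or two in C6c, some computing time (mostly for the optional permutation step, since each kernel is already tuned in every split) and a slightly less favourable stated accuracy. No additional subjects or scans are needed.

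### C6c reworks the classifier only when balanced accuracy falls below about 70%, with no rule for reporting the search, so the final accuracy would be optimistic for new patients

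*Combined protocol and SAP*

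**What the plan says.** The performance target is in C6c (Expected Outcomes and Alternatives): "The model will be especially useful if balanced accuracy reaches ~70" per cent. The next sentence gives the response to a lower result: "If accuracy is below this number, we will investigate refinements or alternatives to our model building techniques". A further fallback follows: "If SVM methods still prove intractable, we are currently developing alternative methods including a random forest approach", with multivariate distance matrix regression (MDMR) named alongside it. Both lists are open-ended.

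The procedure that produces the accuracy is in C6b. Several kernels are compared: "testing a range of kernels such as the linear, polynomial, radial, and sigmoid kernels". On the data split: "The data will be divided into a training set and a test set (70%/30% split, stratified by relapse status". Parameters are tuned by 10-fold cross-validation within the training part. Then: "This procedure will be simulated 10,000 times, from which an optimal kernel and corresponding parameters will be selected".

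C6 also leaves the feature set open: "This set of regions will be adjusted and expanded after preliminary analysis of functional and anatomical measures that statistically separate the four groups".

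C6 to C6d do not mention a locked hold-out, a second cohort, a confidence interval, a permutation test, a cap on attempts or a duty to list every model tried. The only reference to recruiting extra subjects (Expected Outcomes under Hypothesis 1b) concerns image quality.

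**The concern.** The trigger works in one direction. A low estimate leads to more modelling; nothing comparable follows a high one. When several models are tried on one set of subjects and the best is reported, part of its advantage is sampling error that will not recur in new patients.

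The existing safeguard stops short of this step. Cross-validation inside the training set keeps parameter choice away from the test subjects within a run. It cannot protect a switch of method, or a new choice of regions, made because the test accuracy disappointed. If each of the 10,000 repeats redraws the split, which is the natural reading, practically every subject has served in a test set by then, and none is left untouched to judge the rebuilt model.

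This matters because Hypothesis 2a promises a validated classifier and Hypothesis 2b promises phenotypes for later treatment studies. Both need an accuracy that carries over to new patients.

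**Working it through.** **No stated figure to reproduce.** The 70% target comes without a derivation. The power figures in C8 concern group contrasts in fMRI maps, not classifier accuracy.

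**Inputs from the documents.** There are 50 subjects per group (C8), and only AUD and NAUD are followed up (C1, reimbursement paragraph). The relapse model therefore has at most 2 × 50 = 100 subjects before dropout. The benchmark is 0.70 (C6c).

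**Assumptions not in the documents.** Relapse rate 30–50%; three models (the SVM plus the two named alternatives) or ten; correlation between their accuracy estimates 0.5–0.9; equal true accuracy for all models; sensitivity equal to specificity; estimates approximately normal.

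**Step 1: standard error.** With n₁ relapsers, n₀ non-relapsers and true accuracy p, SE = 0.5 × √[p(1−p)(1/n₁ + 1/n₀)].

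- p = 0.65: 0.5 × √[0.2275 × (1/50 + 1/50)] = 0.048 at a 50/50 division; 0.052 at 30/70.
- p = 0.60: 0.049 and 0.053 respectively.

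**Step 2: one model.** P(estimate ≥ 0.70) = 1 − Φ[(0.70 − p)/SE].

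- p = 0.65: z = 0.05/0.0477 = 1.05, giving 15%; z = 0.05/0.0520 = 0.96, giving 17%.
- p = 0.60: z = 2.04, giving 2%; z = 1.87, giving 3%.

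**Step 3: best of K models.** The maximum of K equally correlated normal estimates was simulated. Ranges cover both relapse rates and correlations from 0.9 (lower end) to 0.5 (upper end).

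| True accuracy | One model | Best of 3 | Best of 10 |
|---|---|---|---|
| 0.65 | 15–17% | 21–34% | 28–56% |
| 0.60 | 2–3% | 4–8% | 5–17% |

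**Step 4: mean optimism.** This is SE × √(1−r) × E[max of K standard normals], where r is the correlation and the expected maximum is 0.846 for K = 3 and 1.539 for K = 10. At p = 0.65 and a 50/50 division:

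- K = 3: 0.0477 × 0.707 × 0.846 = 0.029 at r = 0.5; 0.0477 × 0.316 × 0.846 = 0.013 at r = 0.9.
- K = 10: 0.052 at r = 0.5; 0.023 at r = 0.9.

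Across both relapse rates this is about 1–3 points for three models and 2–6 for ten.

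**Step 5: a simulation closer to C6b.** It used 100 subjects, 50% relapse, 344 features and a kernel ridge classifier in place of the SVM (all assumed), with accuracy averaged over 25 stratified 70/30 splits.

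- Pure noise (150 data sets): mean balanced accuracy was 0.502 for one pre-set model and 0.577 for the best of 60 variants. None reached 0.70.
- Moderate signal (120 data sets, pre-set mean 0.661): the chance of reaching 0.70 rose from 24% to about 33% with the best of 60.
- Pure noise, with features picked on all subjects before splitting: mean 0.766, and 99% of data sets reached 0.70.

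**The case against.** The strongest reply is that C6c is an expectations paragraph. It does not say that the SVM result would be dropped, and investigating alternatives after a weak result is ordinary practice. That the rework uses the same subjects is inferred from silence about any other data. This is fair as to wording. The inference is still the natural one, since no other data set is named, and the missing reporting rule is a real gap.

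The illustration also depends on the number of models and their correlation, neither of which is documented. Strongly correlated models give the lower ends of the ranges, and the split-averaged simulation is milder still. That stands, and it is why ranges are shown.

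Four stronger readings are tempting, and the documents do not support them:

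- A reader might infer that 70% is a success criterion, so that the search inflates type I error. C6c presents it as an approximate level of usefulness; no test is attached.
- A reader might infer that swapping methods would carry pure noise past 70%. In the simulation it did not. That happened only when features were picked on all subjects, which is a separate matter of how regions are selected. It bears on this point only if a refinement re-picks regions that way.
- A reader might infer a fixed sequence of random forest and then MDMR for any result below 70%. The two are listed together, and their condition is that SVM remains intractable.
- A reader might apply the sampling error of a single 30-subject test set. With 10,000 repeats of the split, that is not the natural estimate.

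**Conclusion.** The point holds as a gap in reporting and validation. Following C6c as written would give a selected, and therefore optimistic, accuracy for new patients, and nothing in C6 to C6d corrects or discloses it. The likely size is a few percentage points: about 1–3 for three models and 2–6 for ten, under the stated assumptions on relapse rate, correlation and equal true accuracy. It matters most when true accuracy is just under the target. At 0.65 the chance of showing at least 0.70 rises from 15–17% to 21–34% or 28–56%; at 0.60 it stays at 17% or below. The optimism could be much larger if a refinement re-selects features on all subjects. The harm is an over-stated accuracy, not a false-positive test.

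**What to change.** Amend C6c to state three things:

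1. The SVM pipeline of C6 and C6b, with kernel, parameter and ROI selection all done inside the training data, gives the primary SA2 out-of-sample balanced accuracy. It is reported with a 95% CI whatever its value.
2. Every refinement, random forest or MDMR model tried is listed and reported beside it, on the same outer splits, as exploratory.
3. The best of these receives a permutation p-value in which the whole search, including the choice of regions and method, is repeated on shuffled labels.

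The cost is a few sentences and computing time. The drawback is that a later, better-looking model could not become the headline result without new data.
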